8.1.6 Postsurgery

During the post-surgery recovery period, participants will rest quietly, but will be encouraged not to fall asleep. Participants will be permitted to drink clear liquids following surgery. Participant may incorporate foods according to a soft diet following dosing beginning 60 minutes after dosing. Participants will not be allowed to eat 30 minutes prior to any planned assessments.

In order to qualify for randomization and continue in the trial, participants must have 'moderate' or 'severe' postoperative pain intensity on the Categorical Pain Rating Scale and a score of >5 on the NRS within 4.5 hours of the last suture.

Eligible participants will be assigned a participant randomization number and investigational products will be administered according to a generated randomization schedule (see Section 6.1.1).

Participants who have not met the randomization criteria within 4.5 hours from last suture or 14:30 h (+/- 15 minutes) will not be randomized and may be discharged from the clinic, once deemed eligible by an Investigator. Prior to being released from the clinic, discharge procedures will be reviewed with the participant. When discharged, all participants will need to make prior arrangements for travel and should not drive themselves home.

After the baseline (pre-dose) pain intensity is determined, pain intensity and pain relief will be rated by participants at 0.5, 1, 1.5, 2, 3, 4, 5, 6, 7, 8, 9, 10, 11, 12, 14, (16, 18, 20 if awake), 22 and 24 hours (+/-5 minutes over the first 8 hours; +/-8 minutes from hours 9 through 24) post-dose, and immediately prior to the use of the first dose rescue medication.

Instructions will be provided for use of the two stopwatches. A double-stopwatch method will be used to record time up to 24 hours after dosing for time to "first perceptible pain relief" (stopwatch A) and time to "meaningful pain relief *determined*" (stopwatch B). When the participant is administered study medication (following mouth inspection), the Study Coordinator or designee will start two stopwatches (one designated A and one designated B). The faces of the stopwatches will be covered so that the participant remains blinded to the exact time. To determine the time when the participant begins to perceive pain relief, the participant will be given stopwatch A after dosing and will be instructed to:

Page 38 of 67

"Stop the stopwatch when you first begin to feel any pain-relieving effect whatsoever of the drug. That is, when you first feel a little relief. This does not necessarily mean that you feel completely better, although you might, but when you first feel any difference in the pain that you have now."

The participant will notify the Study Coordinator as soon as this stopwatch is stopped. The elapsed time on stopwatch A will be recorded in the case report form as the time to **first perceptible pain relief**. The participant will then be asked:

"Do you consider the relief you experienced meaningful?"

This answer will be recorded by the study coordinator in the case report form. If the participant answers "Yes" to this question, then meaningful pain relief is confirmed. The time recorded in the case report form for time to **meaningful pain relief confirmed will be the same time recorded as first perceptible pain relief.** The participant will not be given the second stopwatch. If the participant does not consider the relief to be meaningful, (by stating No), the participant will be given a second, covered stopwatch with instructions to:

"Stop this stopwatch when you have meaningful relief, that is, when the relief from the pain is meaningful to you."

The elapsed time on stopwatch B will be recorded in the case report form as time to **meaningful pain relief determined**. Unless meaningful pain relief is achieved, the participant will always have an active stopwatch in front of them.

If the participant never experiences first perceptible pain relief, they will retain stopwatch A for the entire 24-hour evaluation period. If the participant experiences first perceptible pain relief but not any meaningful pain relief (confirmed or determined), they will retain stopwatch B for the remainder of the 24-hour evaluation period.

Participants would be encouraged not to sleep before midnight and if needed, woken for assessments (up to hour 14). Participants will be allowed a 6 hour rest period during the overnight hours of the 24-hour evaluation period and woken for the 22 hour assessment. The order of the pain assessments is Pain Intensity, then Pain Relief, then query about any AEs. At hour 24 or immediately prior to the first dose of rescue medication (if prior to hour 24), study participants will be asked to provide a Global Assessment of investigational product after completion of the other assessments. Additionally, participants will have vital signs taken after surgery, then at 1, 12 and 24 hours (+30 minutes post-surgery; +/-30 minutes from hours 1 through 24) post-dose.

Throughout the treatment period, the participants will be monitored for the occurrence of adverse events. Symptoms will be assessed by spontaneous reporting of AEs and by asking the participants to respond to a non-leading question such as "How do you feel?" or "Are you experiencing any other effects?" All reported or observed AEs will be collected and recorded on the case report form. The information will be based on signs and symptoms reported by the participant or observed by the study personnel staff during clinical evaluation.

Page 39 of 67

If a participant has any clinically significant, trial-related abnormalities at the conclusion of the treatment period, the clinical monitor (or designated representative) should be notified and the participant should be asked to remain at the trial site until such abnormalities are stabilized or resolve. If the participant is unable or unwilling to remain at the trial site, the clinical monitor (or designated representative) should be notified, and the Investigator should make every effort to arrange follow-up evaluations at appropriate intervals to document the course of the abnormalities.

Participants will be allowed the use of ice following the use of rescue medication. Ice will not be permitted for participants prior to randomization until after they have been administered rescue medication (if applicable). If participant has been administered rescue, ice will be given as requested by the participant for 20 minute increments. Upon completion of all trial procedures, participants will be discharged from the trial site. Participants will need to make prior arrangements for travel and should not drive themselves home.

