2.2 Background

Naproxen sodium is the sodium salt of naproxen, an aryl propionic acid derivative in the nonsteroidal anti-inflammatory drugs (NSAID) class. Naproxen exerts its analgesic, antipyretic and anti-inflammatory effects by inhibition of prostaglandin synthesis through its non-selective, reversible inhibition of the cyclo-oxygenase (COX) enzymes. Naproxen inhibits the formation of COX-1 dependent thromboxane synthase, A2 (TXA2), which reduces platelet aggregation, and the COX-2 dependent prostacyclin (PGI2) which play a role

Version 4.0 / 13 Mar 2023

Page 18 of 67

in vasodilation associated with inflammation and prostaglandins (i.e. PGE2) which contribute to sensation of pain (Capone, Tacconelli et al. 2004, Grosser, Theken et al. 2017).

In the United States, naproxen has been marketed as a prescription medication since 1976 under the brand name Naprosyn[®]. Its sodium salt, naproxen sodium, was first sold under the trade name Anaprox[®] in 1980. In 1994, the US FDA approved naproxen sodium tablets (using the brand name Aleve[®]), 220 mg for over-the-counter (OTC) use. Aleve[®] is indicated for the temporary relief of minor aches and pains due to minor pain of arthritis, muscular aches, backaches, menstrual cramps, headaches, toothaches, and the common cold. It also temporarily reduces fever. As an OTC medication, Aleve[®] should not be taken for longer than 10 days for pain or 3 days for fever unless otherwise directed by a physician.

Caffeine is a methyl xanthine, found in plants and is generally consumed as coffee, tea, or cocoa. It is a central nervous system and metabolic stimulant, used to reduce fatigue and enhance mental alertness. It can also stimulate the respiratory center, thereby increasing the rate and depth of respiration. It can also facilitate the performance of muscles. Caffeine has been shown to enhance the effectiveness of various pain relievers, so it is accepted as an adjuvant to analgesics such as acetaminophen, ibuprofen and aspirin (Laska, Sunshine et al. 1984, Sawynok and Yaksh 1993, Diener, Pfaffenrath et al. 2005, Derry, Derry et al. 2014, Derry, Wiffen et al. 2015, Lipton, Diener et al. 2017).

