3.1 Handling of Missing Data

3.1.1 Handling of Missing Data for Efficacy Assessments

Use of Rescue Medication:

In all analyses, for participants who take rescue medication, all pain intensity scores after intake of rescue medication will be imputed by the worse of the baseline or the score assessed immediately before taking rescue medication. All pain relief after intake of rescue medication will be imputed by "no relief" (0).

Missing data for efficacy parameter:

If Participants have missing pain data (i.e., pain intensity or pain relief scores) within the 24 hours period for the collection of pain rating data, but nonetheless complete the 24-hour period, then any missing timepoints will be replaced by a time-weighted average of the previous and the next available values (i.e., a linear interpolation for missing values) of the pain data (pain intensity / pain relief score). Intermittent missing data will only be imputed using linear interpolation method and if needed round down to the nearest whole number for pain relief scores, whereas for the categorical pain intensity the value will be rounded up to the nearest whole number.

Interpolation Formula,

$$y = \frac{y_2 - y_1}{x_2 - x_1} (x - x_1) + y_1$$

Where, and if needed round down to the nearest whole number for pain relief scores, whereas for the categorical paint intensity the value will be rounded up to the nearest whole number. y = missing pain data to be imputed, x = respective timepoint of y. y_1 and y_2 = pre and post available pain score of the missing pain data.

 x_1 and x_2 = respective timepoints of y_1 and y_2 .

If Participants do not complete the pain intensity/pain relief assessments for the full 24 hours, then the primary analysis will be calculated up to the last available timepoint, with no imputation for later timepoints.

In a sensitivity analysis, Participants who drop out of the study early because of a related AE or lack of efficacy will have later missing timepoints imputed using a worst-observation-carried-forward (WOCF) method, in which their worst observation at baseline or any time thereafter is imputed. For Participants dropping out early for any other reason, a last-observation-carried-forward (LOCF) imputation will be used.

No imputation will be done for missing data on stopwatch assessments of perceptible and meaningful pain relief. Instead, if data are missing for those assessments, data will be censored as described in Section 4.1.

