4.1 Endpoint Derivations

Pain Intensity:

Participants will assess their current pain intensity using an 11-point (0: No Pain to 10: Worst possible pain) Numerical Rating Scale (NRS). Each Participant will be instructed to mark the number indicating his or her current pain intensity. Below is pain scale format.

No pain	0	1	2	3	4	5	6	7	8	9	10	Worst possible pain
------------	---	---	---	---	---	---	---	---	---	---	----	---------------------

The Participant is to record pain intensity (NRS) at baseline (i.e., pre-dose). Thereafter, the Participant is to record NRS pain intensity assessment at the following time points during the 24 hours period after baseline:

0.5, 1, 1.5, 2, 3, 4, 5, 6, 7, 8, 9, 10, 11, 12, 14, 16, 18, 20, 22 and 24 hours post-dose, and immediately before each use of rescue analgesia.

Ι	Nominal Ti (hours)
0	0
1	0.5
2	1
3	1.5
4	2
5	3
6	4
7	5
8	6
9	7
10	8
11	9
12	10
13	11
14	12
15	14
16	16
17	18
18	20
19	22
20	24

Private and Confidential Study No 22093 Date: MAR 11, 2024

Pain Intensity Difference:

Pain intensity difference (PID) is to be calculated by subtracting the pain intensity at the post-dose time point from the pain intensity at baseline.

$$PID_i = PI_0 - PI_i$$
; for all i > 0.

Where, PI_0 pain intensity at baseline, PI_i is the PI score at post-dose time point i.

Summed Pain Intensity Difference (SPID):

The summed pain intensity difference (SPID) is to be calculated by multiplying the PID score at each post dose time point by the duration (in hours) since the preceding time point and then summing the values over the relevant time period.

$$SPID_{0-2} = \sum_{i=1}^{4} (T_i - T_{i-1}) * PID_i$$

$$SPID_{0-4} = \sum_{i=1}^{6} (T_i - T_{i-1}) * PID_i$$

$$SPID_{0-6} = \sum_{i=1}^{8} (T_i - T_{i-1}) * PID_i$$

$$SPID_{0-8} = \sum_{i=1}^{10} (T_i - T_{i-1}) * PID_i$$

$$SPID_{6-12} = \sum_{i=8}^{14} (T_i - T_{i-1}) * PID_i$$

$$SPID_{0-12} = \sum_{i=14}^{14} (T_i - T_{i-1}) * PID_i$$

$$SPID_{12-16} = \sum_{i=14}^{16} (T_i - T_{i-1}) * PID_i$$

$$SPID_{16-20} = \sum_{i=16}^{18} (T_i - T_{i-1}) * PID_i$$

CONFIDENTIAL

$$SPID_{12-24} = \sum_{i=14}^{20} (T_i - T_{i-1}) * PID_i$$
$$SPID_{16-24} = \sum_{i=16}^{24} (T_i - T_{i-1}) * PID_i$$
$$SPID_{0-24} = \sum_{i=1}^{20} (T_i - T_{i-1}) * PID_i$$

Where, $T_0=0$, T_i is actual post-dose time, PID_i is the PID score at post-dose time T_i for all i > 0.

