7.7.2 Secondary Endpoint(s)

Analysis of the secondary endpoints will be summarized according to the variable type. The details are presented in the following sections.

SPID from 0 to 2, 4, 6, 12 and 24 hours post-dose (SPID0-2, SPID0-4, SPID0-6, SPID6-12, SPID0-12, SPID12-16, SPID16-20, SPID12-24, SPID16-24 and SPID0-24)

SPID0-2, SPID0-4, SPID0-6, SPID6-12, SPID0-12, SPID12-16, SPID16-20, SPID12-24, SPID16-24, SPID0-24 will be calculated using the formula specified in Section 4.1. The same method that is used for the analysis of the primary endpoint will be used to assess the difference between the treatment groups in each metric.

This endpoint will be analysed using ITT population (without imputation) as primary analysis while PP population (without imputation and single imputation) will be used as secondary to conduct the sensitivity analysis.

In the secondary analysis, endpoint will be imputed as described in Section 3.1.1, if any pain assessments are missing or Participant takes rescue medication.

Total pain relief from 0 to 2, 4, 6, 8, 12 and 24 hours post-dose (TOTPAR0-2, TOTPAR0-4, TOTPAR0-6, TOTPAR 6-12, TOTPAR0-8 TOTPAR0-12, TOTPAR12-16, TOTPAR16-20, TOTPAR 12-24, TOTPAR16-24 and TOTPAR0- 24)

TOTPAR0-2, TOTPAR0-4, TOTPAR0-6, TOTPAR 6-12, TOTPAR0-8 TOTPAR0-12, TOTPAR12-16, TOTPAR16-20, TOTPAR 12-24, TOTPAR16-24 and TOTPAR0- 24 will be calculated using the formula specified in Section 4.1. These secondary efficacy endpoints will be analyzed using an analysis of covariance (ANCOVA) model, which will include TOTPAR as dependent variable, treatment as main effect and baseline pain intensity (Numerical Rating Score) as the covariate. The least square (LS) mean, standard error (SE) and 95% confidence interval (CI) of LS mean for each treatment group will be reported.

In addition, the least square mean difference, SE, 95% Confidence interval of LS mean difference and p-value for all pairwise treatment group (include placebo) comparisons will be reported. Descriptive statistics (including n, mean, SD, median, minimum, and maximum) for TOTPAR will also be presented by treatment group.

ITT population (without imputation) will be used as the primary analysis for this endpoint while PP population (without imputation and single imputation) will be used as secondary to conduct the sensitivity analysis.

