The definitions and censoring rules are defined in Section 4.1. Median time will be compared between the treatment groups and placebo using a log-rank test stratified by baseline pain intensity (Categorical pain intensity), pair wise comparison will be made using Tukey-Kramer method and adjusted P-value will be reported. The summary statistics (25th percentile, Median, 75th percentile and it 95% CI) and overall K-M estimates with 95% CI will be presented by treatment groups. The analysis will be performed for the ITT Population.

Pain Intensity Difference (PID) and Pain Relief scores at 0.5, 1, 1.5, 2, 3, 4, 5, 6, 7, 8, 9, 10, 11, 12, 14, (16, 18, 20 if awake), 22 and 24 hours post-dose

The PID at each scheduled time point will be calculated using the formula specified in Section 4.1. Descriptive statistics (n, mean, SD, median, minimum, and maximum) will be presented by treatment groups.

Pain Relief score categories will be presented in the form of frequency counts and percentage by treatment groups and overall. Also, the pain relief score at each scheduled time point will be summarised using descriptive statistics (n, mean, SD, median, minimum, and maximum) by treatment groups. The analysis will be performed for the ITT Population.

A graphical illustration of the time effect curve (Time versus Mean PID / Mean pain relief score) will be presented.

Analysis of Peak Pain Intensity Difference (Peak PID)

The peak PID for each Participant will be identified using the description given in Section 4.1.

The Peak Pain Intensity Difference over the entire study (Peak PID0-24) will be summarized by treatment group using descriptive statistics (n, mean, SD, median, minimum, and maximum) and analyzed using an analysis of covariance (ANCOVA) model, which includes Peak PID0-24 as dependent variable, treatment as main effect and baseline pain intensity (Numerical Rating Score) as the covariate. The least square (LS) mean, standard error (SE) and 95% confidence interval (CI) of LS mean will be reported for each treatment group. In addition, the least square mean difference, SE, 95%

Confidence interval of LS mean difference and p-value for all pairwise treatment group (include placebo) comparisons will be reported. The analysis will be performed for the ITT Population.

Analysis of Peak Pain Relief

The peak pain relief for each Participant will be identified using the description given in Section 4.1.

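### Ratings missed through sleep at 16, 18 and 20 h have no single consistent rule: by-time means may drop unrescued sleepers but keep rescued participants, and interpolated relief is rounded down

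*Protocol*

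**What the plan says.** **Schedule.** Protocol 8.1.6 gives the late ratings as "16, 18, 20 if awake), 22 and 24 hours (+/-5 minutes over the first 8 hours; +/-8 minutes from hours 9 through 24) post-dose". On waking it says "Participants would be encouraged not to sleep before midnight and if needed, woken for assessments (up to hour 14"), followed by "Participants will be allowed a 6 hour rest period during the overnight hours of the 24-hour evaluation period and woken for the 22 hour assessment". A sleeper can therefore go from 14 h to 22 h without a rating. SAP 4.1 lists the times as "0.5, 1, 1.5, 2, 3, 4, 5, 6, 7, 8, 9, 10, 11, 12, 14, 16, 18, 20, 22 and 24 hours post-dose" without the awake condition, although SAP 5.2 and 7.7.2 keep it. No SAP rule deals with sleep as such.

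**Filling in.** SAP 3.1.1 (and protocol 9.4.1) replaces every score after rescue, in all analyses: pain intensity by the worse of baseline and the pre-rescue score, relief by 0. For participants who complete 24 h, SAP 3.1.1 interpolates other missing ratings linearly between neighbours, with the instruction "if needed round down to the nearest whole number for pain relief scores".

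**Use.** SPID12-16, 16-20 and 16-24 and the matching TOTPAR windows are secondary endpoints. For the SPID windows SAP 7.7.2 says "The same method that is used for the analysis of the primary endpoint will be used to assess the difference between the treatment groups in" those measures, and TOTPAR gets the same ANCOVA. For the single time points, "A graphical illustration of the time effect curve (Time versus Mean PID / Mean pain relief score) will be presented".

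**Imputation labels.** SAP 7.7.1 and 7.7.2 call the ITT analyses of SPID and TOTPAR unimputed, and a few lines later say they are imputed under 3.1.1. The SAP 7.7.3 table marks those rows, and the by-time PID and relief row, as having no imputation. The by-time text in 7.7.2 has no link to 3.1.1.

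**The concern.** A participant who rescued before 16 h has a value at 16, 18 and 20 h whether asleep or awake. One who has not rescued has a value only if awake or if interpolation is applied. The missing ratings therefore belong to participants whose relief was enough to avoid rescue and to sleep.

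If the by-time summaries apply the rescue rule but not interpolation, the curves dip at 16, 18 and 20 h and recover at the compulsory 22 h rating, and arm differences at those times can be distorted. If interpolation is applied, relief is rounded in one direction only, and SPID/TOTPAR16-20 may contain no rating made in that window. Duration of effect is a stated secondary objective, and these curves and windows are among the results a reader would consult for it.

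**Working it through.** **Plan's own figure.** The documents give no figure for the share asleep or for the late windows. The one calculation is for SPID0-8 (difference 6.5, SD 16.9, 144 per main arm, 90% power). It reproduces: two-sided noncentral t at 144 per arm gives 90.2%. SPID0-8 uses no awake-only rating.

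**1. By-time means.** After rescue the imputed intensity is at least the baseline score, so PID is 0 or negative. Assume PID 0 if rescued, PID 4 if unrescued (asleep or awake), an unrescued share u of 0.5 in one arm and 0.2 in the other, and a share s of the unrescued asleep and left missing, equal in both arms. None of these inputs comes from the documents.

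True mean = 4u: 2.00 and 0.80, difference 1.20.

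Displayed mean = 4u(1-s) / [(1-u) + u(1-s)]:

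| s | u = 0.5 | u = 0.2 | Difference shown |
|---|---|---|---|
| 0.3 | 1.40/0.85 = 1.65 | 0.56/0.94 = 0.60 | 1.05 |
| 0.7 | 0.60/0.65 = 0.92 | 0.24/0.86 = 0.28 | 0.64 |
| 0.9 | 0.20/0.55 = 0.36 | 0.08/0.82 = 0.10 | 0.27 |

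**2. Rounding down.** With ratings at 14 h and 22 h only, the interpolated 18 h value is the midpoint, and the 20 h value is a quarter of the 14 h score plus three quarters of the 22 h score. For the window as named, TOTPAR16-20 = 2 × (18 h) + 2 × (20 h).

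| Relief at 14 h, 22 h | Unrounded | Rounded down | Change |
|---|---|---|---|
| 3, 4 | 2(3.5) + 2(3.75) = 14.5 | 2(3) + 2(3) = 12 | -17% |
| 4, 3 | 2(3.5) + 2(3.25) = 13.5 | 2(3) + 2(3) = 12 | -11% |
| 2, 1 | 2(1.5) + 2(1.25) = 5.5 | 2(1) + 2(1) = 4 | -27% |
| 4, 4 | 16 | 16 | 0 |

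Rescued participants are fixed at 0 and lose nothing. A time-weighted sum does not need whole numbers, and 3.1.1 sets no rounding for the NRS; its round-up concerns categorical intensity, which is a pre-dose scale.

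**3. Weights when 16, 18 and 20 h are all missed.** The 14 h/22 h weights are 0.75/0.25 at 16 h, 0.5/0.5 at 18 h and 0.25/0.75 at 20 h. Each interval is 2 h, and windows are as named.

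- SPID16-20 = 2(0.5 + 0.25) PID14 + 2(0.5 + 0.75) PID22 = 1.5 PID14 + 2.5 PID22. All of it comes from outside the window.
- SPID12-16 = 3.5 PID14 + 0.5 PID22. Outside share 0.5/4 = 12.5%.
- SPID16-24 = 1.5 PID14 + 4.5 PID22 + 2 PID24. Outside share 1.5/8 = 19%.

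The summation limits printed in SAP 4.1 start these windows one interval early. With them SPID16-20 becomes 3 PID14 + 3 PID22, still wholly outside.

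If the 20 h rating is obtained, SPID16-20 = 0.67 PID14 + 3.33 PID20, and the outside share falls to 0.67/4 = 17%.

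Interpolation is itself an assumption. With PID14 = 4 and PID22 = 0 it gives 1.5 × 4 = 6. The true value is 16 if PID stayed at 4 to 20 h, and 0 if relief ended before 16 h.

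**The case against.** The strongest reply is that part 1 mixes two readings. The rescue rule and the interpolation rule both sit in SAP 3.1.1, and interpolation is written for any missing time point. The no-imputation label also stands on the SPID and TOTPAR rows, to which 7.7.1 and 7.7.2 apply 3.1.1, so it may mean only that worst- or last-observation carry-forward is not used. The per-protocol rows, which set no imputation against single imputation, fit that reading. A fully literal reading would leave observed post-rescue scores in place too. This stands as far as it goes: the mixed reading is not the declared plan. It remains open because the rescue rule is said to hold in all analyses and the by-time text lacks the link that SPID and TOTPAR have.

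It is also fair that the all-missed case is a worst case. Dosing can run to about 14:30, which puts 18 h and 20 h at 08:30 and 10:30. Only three of twenty post-dose times are affected.

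Some stronger readings are tempting but unsupported:

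- *Wakefulness depends on treatment.* The protocol says of caffeine "It is a central nervous system and metabolic stimulant, used to reduce fatigue and enhance mental alertness", but nothing shows an effect 16 to 20 h after one dose. The illustration uses the same sleep share in both arms.
- *The dip is largest where most participants are unrescued sleepers.* At s = 0.7 the loss is 1.08 for u = 0.5 but 0.68 for u = 0.9 (3.60 to 2.92).
- *Longer-lasting arms lose the most TOTPAR.* Stable relief loses nothing, and fading relief can lose proportionally more.
- *The late windows should lose their p-values in favour of 12-24.* SPID12-24 and SPID16-24 each put 50% of their weight on awake-only ratings (6 of 12 h; 4 of 8 h).

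**Conclusion.** The point holds for the three awake-only times and the summaries built on them. The SAP contradicts itself on whether SPID and TOTPAR are imputed, and leaves the by-time means open to a reading that drops unrescued sleepers and keeps rescued participants. On that reading the 16, 18 and 20 h means are biased downward whenever the omitted sleepers have a higher mean PID than those who remain. The size depends on rescue and sleep shares that the documents do not give, so the 1.05, 0.64 and 0.27 are illustrations only.

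The round-down is a definite rule. It lowers TOTPAR for unrescued participants with a missed rating whenever interpolation between unequal neighbours gives a fraction. SPID/TOTPAR16-20 is wholly out of window only when all three ratings are missed; SPID/TOTPAR12-16 and 16-24 are much less exposed.

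A reader might infer that the trial's conclusion on duration is undermined. The documents do not support that: duration is not tied to these windows, and time to first rescue and cumulative rescue are also secondary endpoints. The formal test sequence covers SPID0-8 only. The sleep gap affects neither SPID0-8, its power nor time to rescue, although the contradictory label also stands on the SPID0-8 row.

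**What to change.** 1. In SAP 7.7.1, 7.7.2 and 7.7.3, replace the no-imputation wording for SPID, TOTPAR and by-time PID and relief with one statement: the 3.1.1 rescue rule and linear interpolation apply, and worst- and last-observation carry-forward do not. Apply this to the means and curves at 16, 18 and 20 h, and mark those points as partly interpolated.
2. Delete the round-down for interpolated relief in TOTPAR and keep decimals.
3. Report by arm, at 16, 18 and 20 h, how many ratings were observed, interpolated and rescue-imputed. Note beside SPID/TOTPAR16-20 that the result may rest largely on the 14 h and 22 h ratings.
4. Keep the planned ANCOVA for the other late windows, and record the change in SAP 7.13, which now states that there are none.

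The cost is SAP wording, some programming and one extra table. No new data are needed and the overnight schedule does not change. The remaining limitation is that interpolation assumes a straight line between 14 h and 22 h; the counts show how much depends on it.
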